4.3 Safety Population

The safety Population (SAF) includes all patients with at least one study treatment administration.

All safety assessment analysis will be done in the safety population. In addition, the primary and secondary endpoint analysis will be repeated using the safety population.

Safety assessments include vital signs, physical examinations, adverse event (AE) and ADE (adverse device effect) review, and clinical laboratory tests.

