4.4 Completer Population

The Completer Population includes all patients who complete the 4-week treatment period (Week 5).

The analyses of the primary, secondary and exploratory endpoints will be repeated using this population.

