5.1.3 Determination of Sample Size

A sample size of 52 patients will have 80% power to detect a change from baseline to Week 5 of at least 0.35 points in the Wound-QoL global score (e.g., a baseline mean Wound-QoL global score of 3.53 and a follow-up mean Wound-QoL global score of 3.18), assuming an estimated SD of differences of 0.88, using a paired t-test with a 0.050 two-sided significance level. Patients who withdraw or are withdrawn before completion of the Week 2 assessments and the Week 3 Wound-QoL questionnaire will be replaced to ensure that at least 52 patients will complete the study.

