5.1.4 Time Windows

In this post-marketing study, data will be collected from each patient at screening, baseline (Week 1), Week 2, Week 3, Week 4 and Week 5 (final visit). The Week 1 baseline visit will be scheduled at ≤ 1 week after screening visit with a window of ± 1 day. For the visits Week 2 up to Week 5, a window of ± 1 day will be allowed for patient data collection.

All patients are to adhere to the visit schedule as specified in the flowchart (Table 1). If any visit or assessment has to be rescheduled and deviates from the given time window, this visit or assessment, will be handled as out of window. Subsequent visits should follow the original visit date schedule. Out of window and unscheduled assessments will be listed, but not used for descriptive analysis and calculation of primary and secondary endpoints.

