5.1.7 Demographics and Baseline Wound History Characteristics

Patients demographics are age [years], weight [kg], height [cm], body mass index (BMI) [kg/m²], sex, race, and ethnicity.

All data as recorded in the eCRF are used for the analyses of patient demographics.

Regarding age, the age at the time of the baseline visit is recorded in the eCRF.

Categorical patient baseline wound history variables are:

- 1) Wound type
 - Venous Ulcer
 - Arterial Ulcer
 - Diabetic Ulcer
 - Burn (1st or 2nd Degree)
 - Cellulitis
 - Soft Tissue Necrosis
 - Neuropathic Ulcer
 - Traumatic Ulcer
 - Collagen Vascular
 - Infectious

- 2) Wound description
 - Partial Thickness Wound
 - Full Thickness Wound

- 3) Wound location
 - Left leg
 - Right leg
 - Left foot
 - Right foot

4) Wound location on the leg or foot

- Medial
- Lateral
- Anterior
- Posterior

5) Past complications

- Infection
- Recurrent Hospitalizations
- Others

Patient demographic and baseline background information will be summarized in tables for the safety, evaluable and completer population.

Descriptive statistics (sample size, mean, median, standard deviation [SD], minimum [Min] and maximum [Max]) will be presented for continuous variables: age, body mass index [BMI], height, weight, wound age, and wound surface area. Frequency counts and percentages will be tabulated for categorical variables: gender, ethnicity, race, and baseline target wound history and characteristics categories. As each subject may have 2 chronic wounds, which will be treated and assessed, we will need to distinguish between the 2 wounds for the purpose of descriptive analysis (i.e. wound #1 and wound #2). Baseline target wound characteristics will also be listed in order to include a description of other past complications. Only 1 wound must meet all of the inclusion/exclusion criteria.

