5.2.1 Primary Analysis

The primary endpoint is defined as

- Change from baseline to Week 5 in the global score of the Wound-QoL questionnaire.

The primary endpoint will be analysed by the following primary analysis in the evaluable and completer populations.

Let μ be defined as expected value of change from baseline to Week 5 in the global score of the Wound-QoL questionnaire.

The null hypothesis to be tested is that μ is equal to 0, i.e., no score change from baseline. The alternative hypothesis is that μ is different from 0. i.e.:

$H_0: \mu = 0$ vs. $H_1: \mu \neq 0$.

The null hypotheses will be tested using a paired t-test statistic. The t-test is conducted using Proc MEANS procedure in SAS version 9.4. The null hypothesis will be rejected at a two-tailed significance level of 0.05.

In addition, descriptive statistics (n, mean, SD, median, min, max) will be provided in the evaluable population for the primary endpoint. Associated the 95% CI and p-value will be presented for the change from baseline to Week 5 in the global score of the Wound-QoL questionnaire.

The primary endpoint analysis will also be repeated using the safety and completer populations.

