5.2.5 Other Variables

There will be no hypothesis test for other variables, thus all of them will be conducted based on descriptive statistics. The other variables to be analysed are:

- Weekly global score and its change from baseline in Wound-QoL questionnaire
- Weekly Body subscore, Psyche subscore, and Everyday Life subscore and their change from baseline in Wound-QoL questionnaire
- Weekly appearance and size of wound(s)
- Weekly proportion of patients with no score of 3 or 4 given in each individual item in Wound-QoL questionnaire

The continuous variables global scores and size of wound(s) will be analysed by the summary statistics by week (weeks 1, 2, 3, 4, 5) with the number of patients (n), mean, SD, median, minimum, and maximum.

For categorical variable appearance of wound(s), frequency counts and percentages will be used to summarize the results by week. The number of non-missing values will be used as denominator in percentage calculations.

The first two analyses above will be conducted in the evaluable, safety and completer populations whereas the last two analyses will be conducted in the evaluable and completer populations.

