6. TABLES, LISTINGS, AND FIGURES

Table of Contents for OPM-G-H-1506

Tables

	1. Subject disposition
Table 1	Overall patient disposition including reasons for exclusion from analysis populations– Enrolled population
	2. Protocol deviations
Table 2	Protocol deviations – Safety Population and Evaluable Population
	3. Demographic and baseline characteristics
Table 3	Demographic and baseline characteristics – Safety Population and Evaluable Population
	4. Wound history
Table 4	Wound History – Safety Population and Evaluable Population
	5. Study medication exposure and compliance
Table 5.1	Treatment and exposure to study product under this protocol – Safety Population
Table 5.2	Treatment and exposure to study product under this protocol – Evaluable Population
	6. Efficacy – Wound-QoL questionnaire scores
Table 6.1	Wound-QoL global scores and changes from baseline by week – descriptive statistics and paired t-test for week 5 – Evaluable Population
Table 6.2	Wound-QoL Body subscores and change from baseline by week – descriptive statistics – Evaluable Population
Table 6.3	Wound-QoL Psyche subscores and change from baseline by week – descriptive statistics – Evaluable Population
Table 6.4	Wound-QoL Everyday Life subscores and change from baseline by week – descriptive statistics – Evaluable Population
Table 6.5	Wound-QoL global scores and changes from baseline by week – descriptive statistics and paired t-test for week 5 – Safety Population
Table 6.6	Wound-QoL Body subscores and change from baseline by week – descriptive statistics – Safety Population
Table 6.7	Wound-QoL Psyche subscores and change from baseline by week – descriptive statistics – Safety Population
Table 6.8	Wound-QoL Everyday Life subscores and change from baseline by week – descriptive statistics – Safety Population
Table 6.9	Wound-QoL global scores and changes from baseline by week – descriptive statistics and paired t-test for week 5 – Completer Population

Table 6.10	Wound-QoL Body subscores and change from baseline by week – descriptive statistics – Completer Population
Table 6.11	Wound-QoL Psyche subscores and change from baseline by week – descriptive statistics – Completer Population
Table 6.12	Wound-QoL Everyday Life subscores and change from baseline by week – descriptive statistics – Completer Population
	7. Efficacy - Wound assessment
Table 7.1	Wound assessment– descriptive statistics – Evaluable Population
Table 7.2	Wound assessment– descriptive statistics – Completer Population

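### The Safety and Completer repeats of the Week 5 paired t-test cannot show or correct dropout bias, because the SAP has no method for a missing Week 5 score and no rule for the early discontinuation score

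*SAP*

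**What the plan says.** SAP 5.2.1 defines the primary endpoint as the change from baseline to Week 5 in the global score: "The null hypotheses will be tested using a paired t-test statistic". The main analysis is in the Evaluable Population (SAP 4.2), which requires at least two weeks of treatment and a completed Week 3 questionnaire, but no Week 5 score.

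Two repeats are planned. For the Safety Population (at least one treatment), SAP 4.3 says: "In addition, the primary and secondary endpoint analysis will be repeated using the safety population". For the Completer Population, SAP 4.4 says: "The analyses of the primary, secondary and exploratory endpoints will be repeated using this population". The results go to Tables 6.1, 6.5 and 6.9.

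SAP 5.1.2 is the section on dropouts and missing data. It covers item scoring, the early discontinuation visit and the replacement of early withdrawals. It does not say what happens when the Week 5 global score is missing. SAP 5.1.4 allows one day either side of each visit and adds: "Out of window and unscheduled assessments will be listed, but not used for descriptive analysis and calculation of primary and secondary endpoints".

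The protocol treats early discontinuation as a form of the Week 5 visit, with the questionnaire completed first (Protocol 9.2.5 and Table 1). Attendance is asked for where possible (Protocol 7.4). The SAP does not say whether that score counts as Week 5.

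Scores from the other weeks are summarised descriptively under SAP 5.2.5: "Weekly global score and its change from baseline in Wound-QoL questionnaire", in all three populations.

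**The concern.** A paired t-test uses a patient only if both scores exist. Changing the population label does not bring in patients who have no usable Week 5 score. A treated patient who leaves early belongs to the Safety Population by definition but, under SAP 5.1.4, not to its test.

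The protocol gives reason to think that leaving may be related to outcome. A patient whose wound becomes infected and who needs a prohibited medication is discontinued (Protocol 8.4.2), and adverse events or a change in condition are listed grounds for withdrawal (Protocol 7.3). Patients who leave after the Week 3 form remain in the Evaluable Population and are not replaced, yet they supply no pair.

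In a single-arm test against zero change, losing patients who are doing badly moves the estimate towards improvement. If all three tests share that loss, their agreement could be taken as support that they cannot give.

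**Working it through.** **1. The plan's own figure.** SAP 5.1.3 says: "A sample size of 52 patients will have 80% power to detect a change from baseline to Week 5 of at least 0.35 points", with an SD of differences of 0.88 and two-sided alpha of 0.05. The noncentrality is 0.35 / 0.88 × √52 = 2.87, and the noncentral t distribution gives power of 80.3% (n = 51 gives 79.5%). The sample size reproduces and is not in question. Fewer usable pairs would lower power: 76.1% with 47 and 71.1% with 42.

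**2. Who supplies a pair, if early discontinuation scores do not count as Week 5.**
- Safety test: treated, with a baseline and an in-window Week 5 score.
- Completer test: essentially the same patients, since an in-window Week 5 score means that the end of treatment was reached.
- Evaluable test: those patients minus any who missed the Week 3 form.

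In simulations of 60 treated patients, the Evaluable and Safety pairs were identical in every run when no Week 3 form was missed. With 5% or 10% of those forms missed (assumed), they were identical in about 5–9% or 0–1% of runs, and the Safety and Completer tests regained about 2 to 6 patients. None of those regained was an early leaver.

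**3. What the repeats would hide.** Assume that completers change by −0.35 (negative is improvement), a fraction d leaves, and leavers change by c. All three tests then expect −0.35, while the mean over all treated patients is (1 − d)(−0.35) + d·c.

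| d | c = 0 | c = +0.35 |
|---|---|---|
| 5% | −0.333 | −0.315 |
| 10% | −0.315 | −0.280 |
| 20% | −0.280 | −0.210 |

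The hidden difference is about 0.02 to 0.14 points.

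**4. Effect on the test when nothing has changed.** Assumptions: true mean change 0 at every week, SD 0.88, AR(1) correlation r between adjacent weeks, and leavers who are exactly the patients with the worst Week 3 change, so that 52 pairs remain. There were 4,000 simulated trials per row.

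| r | Leavers / treated | Mean Week 5 change in the pairs | Rejection at 5% |
|---|---|---|---|
| 0.6 | 5 / 57 | −0.055 | 8.1% |
| 0.6 | 8 / 60 | −0.077 | 10.5% |
| 0.6 | 13 / 65 | −0.107 | 14.7% |
| 0.8 | 5 / 57 | −0.093 | 13.5% |
| 0.8 | 8 / 60 | −0.134 | 21.6% |
| 0.8 | 13 / 65 | −0.195 | 40.9% |

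Repeating the simulation gave 0.05 to 0.19 points and 7% to 39%, so the ranges are about 0.05 to 0.20 and 7% to 41%.

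The means can be checked by hand. The stayers' mean Week 3 change is about −0.15, −0.21 and −0.30 for 5, 8 and 13 leavers, and it carries to Week 5 with factor r². For r = 0.6, 0.36 × (−0.15, −0.21, −0.30) = −0.054, −0.076, −0.108. For r = 0.8, 0.64 × the same values = −0.096, −0.134, −0.192.

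Predicting the leavers' Week 5 change from their Week 2 and 3 scores returns a mean between −0.001 and 0.004.

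**5. If the early discontinuation score did count as Week 5.** Take 20% dropout, leavers at 0, half of them gone before Week 3, no Week 3 form missed, and every leaver attending the visit. Of 60 treated patients, 48 complete and 6 leavers are Evaluable. The expected means are 48 × (−0.35) / 54 = −0.311 (Evaluable), 48 × (−0.35) / 60 = −0.280 (Safety) and −0.350 (Completer). Simulation gave −0.312, −0.281 and −0.352, so the repeats would then differ.

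**The case against.** The best defence rests on the early discontinuation visit. The protocol files it under Week 5, and SAP 5.1.4 speaks of visits that had to be rescheduled without naming early discontinuation. If the score counts, the Safety repeat includes the leavers who attended. This stands: a reader might infer that leavers contribute nothing under any reading, and the documents do not settle that.

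A reader might also infer that all three tests use identical pairs. They need not, because the Evaluable set omits patients who missed the Week 3 form and the other two do not.

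Nor is the plan blind to selective loss. Tables 6.1, 6.5 and 6.9 show change by week in each population. In the case of step 4, the Completer mean at Week 3 would be −0.15 to −0.30, against 0 in the other two, which is a visible gap. That information is descriptive, however, and gives no Week 5 estimate.

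The illustration also favours the remedy. Dropout determined by the observed Week 3 score is exactly what a missing-at-random method can correct, so the near-zero result is built in; it also came from a regression prediction, not from the model proposed here.

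Finally, SAP 5.1.1 calls the test exploratory, and the SAP nowhere labels the repeats as robustness checks. Both limit the consequence, although SAP 5.2.1 still rejects at 0.05 and reports a p-value.

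**Conclusion.** The concern holds for the Week 5 tests. With no method for a missing Week 5 score, and with SAP 5.1.4 read as excluding early scores, the Safety and Completer tests use essentially the same pairs. The Evaluable test uses those pairs less any patients without a Week 3 form. No leaver enters, so the repeats can neither reveal nor correct selective dropout. The weekly tables offer only indirect, untested evidence.

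The conclusion is conditional on the early discontinuation rule, which the SAP leaves open.

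The size is illustrative: about 0.05 to 0.20 points of apparent improvement, set against a planned effect of 0.35, and rejection in about 7% to 41% of trials with no true change. A reader might take 41% as the trial's false-positive rate. It is not: it needs 13 of 65 patients lost strictly by worst score and a weekly correlation of 0.8, and the documents give no dropout rate. If dropout is unrelated to score, the estimate is unbiased.

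A minor mismatch goes with this. SAP 5.1.7 promises: "Patient demographic and baseline background information will be summarized in tables for the safety, evaluable and completer population". The list in SAP 6 gives Table 3 as: "Demographic and baseline characteristics – Safety Population and Evaluable Population", and Table 4 likewise omits completers. That does not mean completers' baseline data are absent: Table 6.9 would include their baseline global score, and Listing 4 gives patient-level data.

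**What to change.** Keep the paired t-test in the Evaluable Population as primary, and keep both planned repeats.

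1. In SAP 5.1.2 and 5.1.4, state that an early discontinuation score is assigned to the scheduled week whose window it falls in, and is not treated as Week 5 unless it falls in the Week 5 window. A score that falls in no window stays listed only, as SAP 5.1.4 already provides.
2. In SAP 5.2.1 and Table 6.5, add a supportive mixed model for repeated measures in the Safety Population. The response is the change in global score at Weeks 2 to 5, with categorical week, centred baseline and unstructured covariance. Include every treated patient with a baseline and at least one later score, and report the Week 5 estimate with its 95% CI.
3. Report the number of pairs behind each paired test and how many come from patients who left early. Do not present agreement among the three tests as evidence against dropout bias.
4. Add the Completer columns to Tables 3 and 4.

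The cost is SAP wording and one model on scores already collected, with no new visits or patients. The downside is a missing-at-random assumption in a supportive analysis: the model cannot account for worsening after a patient's last score, and it omits patients with no score after baseline. With no missing scores it gives essentially the paired t-test result.

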4.4 Completer Population

The Completer Population includes all patients who complete the 4-week treatment period (Week 5).

The analyses of the primary, secondary and exploratory endpoints will be repeated using this population.

5. STATISTICAL METHODOLOGY

5.1 Statistical and Analytical Issues

5.1.1 Statistical Methods

All data will be summarized, and where necessary, data will also be listed. For continuous variables, data will be summarized with the number of patients (n), mean, SD (standard deviation), median, minimum, and maximum. For categorical variables, data will be tabulated with the number and proportion of patients for each category.

For the primary analysis of the change from baseline to Week 5 in the global score of the Wound-QoL questionnaire, a paired t-test will be performed using PROC MEAN procedure in

SAS version 9.4. This inferential statistical analyses comparing global score change will be interpreted in an exploratory sense only at an alpha level of 5% for statistical significance.

5.1.2 Handling of Dropouts and Missing Data

Patients who prematurely withdraw from the study for any reason should complete the early discontinuation visit requirements. If the early discontinuation visit is not done, the reason(s) will be recorded in the eCRF. Patients who withdraw or are withdrawn before completion of the Week 2 assessments and the Week 3 Wound-QoL questionnaire will be replaced to ensure that at least 52 patients will complete the study.

The questionnaire consists of 17 statements of impairments. The patient assesses and documents the degree to which the impairments affected him/her within the previous 7 days by ticking checkboxes using a Likert scale from 0 to 4: 0=not at all, 1=a little, 2=moderately, 3=quite a lot, 4=very much. The global score is an average of the completed questionnaire items, which can be calculated if at least 13 out of 17 items are completed.

If more than 1 box is checked within an item, or if a patient has checked between 2 checkboxes, the item is treated as missing. Missing items are not averaged in the global score. A global score can be computed only if at least 75% of the items have been answered and are not treated as discarded or as missing (at least 13 of the 17 items are valid), and a subscore (Body, Psyche, and Everyday Life) can be computed only if no more than 1 item of the subscale is missing.

5.1.3 Determination of Sample Size

A sample size of 52 patients will have 80% power to detect a change from baseline to Week 5 of at least 0.35 points in the Wound-QoL global score (e.g., a baseline mean Wound-QoL global score of 3.53 and a follow-up mean Wound-QoL global score of 3.18), assuming an estimated SD of differences of 0.88, using a paired t-test with a 0.050 two-sided significance level. Patients who withdraw or are withdrawn before completion of the Week 2 assessments and the Week 3 Wound-QoL questionnaire will be replaced to ensure that at least 52 patients will complete the study.

5.1.4 Time Windows

In this post-marketing study, data will be collected from each patient at screening, baseline (Week 1), Week 2, Week 3, Week 4 and Week 5 (final visit). The Week 1 baseline visit will be scheduled at ≤ 1 week after screening visit with a window of ± 1 day. For the visits Week 2 up to Week 5, a window of ± 1 day will be allowed for patient data collection.

All patients are to adhere to the visit schedule as specified in the flowchart (Table 1). If any visit or assessment has to be rescheduled and deviates from the given time window, this visit or assessment, will be handled as out of window. Subsequent visits should follow the original visit date schedule. Out of window and unscheduled assessments will be listed, but not used for descriptive analysis and calculation of primary and secondary endpoints.

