	
[PHMB]), and sodium hydroxide for pH adjustment. In this study, the 350-mL squeeze bottle will be used.
 
Prontosan Wound Gel is a clear, colorless gel containing glycerol, hydroxyethylcellulose, 0.1% undecylenamidopropyl betaine, 0.1% PHMB, and purified water; it is packaged in a 30-mL squeeze bottle.
 
The frequency and method of Prontosan solution and Prontosan gel applications will be per the institutional guidelines and the Prontosan IFU for the individual patient wound(s).

Reference Device:	Not applicable
Treatment Duration:	Each patient will receive 4 weeks of study treatment.
Criteria for Evaluation:	
Patient QoL will be evaluated from the global score and the subscores (Body, Psyche, Everyday Life) of the Wound-QoL questionnaire to be assessed at Week 0 (screening visit) for eligibility, and at Weeks 1 (baseline visit), 2, 3, 4, and 5 (end of treatment or early discontinuation visit). Wound size(s) will be measured with standard, single-use, disposable rulers at Week 0 (screening visit) for eligibility; and measured with standard, single-use, disposable rulers and documented with digital photography before and after study treatment at Weeks 1 (baseline visit), 2, and 5. At screening, the Investigator will assess wound history for the wound(s) (wound type, wound age, location, past complications, and current dressing change frequency). At all visits, the Investigator will assess the wound(s) appearance, granulation tissue, exudate, drainage, surrounding erythema and/or swelling, and any signs of infection.
 
Safety will be evaluated from AEs, ADEs, and physical examinations.

Study Endpoints:
	
Primary Endpoint
 
 • Change from baseline to Week 5 in the global score of the Wound-QoL questionnaire 
Secondary Endpoints
 
 • Change from baseline to Week 5 in the Body subscore of the Wound-QoL questionnaire • Change from baseline to Week 5 in the Psyche subscore of the Wound-QoL questionnaire • Change from baseline to Week 5 in the Everyday Life subscore of the Wound-QoL questionnaire 
Exploratory Endpoint
 
 • Change from baseline to Week 5 in the appearance and size of the wound(s)

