12 STATISTICAL ANALYSIS

A Statistical Analysis Plan (SAP) will be prepared after the protocol and eCRF are approved. This document will provide further details regarding the definition of analysis variables and analysis methodology to address all study objectives. The SAP will serve as a complement to the protocol and supersedes it in the case of any differences.

The statistical evaluation will be performed using the Statistical Analysis Software (SAS®) Version 9.2 or higher (SAS Institute, Cary, NC). All data will be summarized using descriptive statistics, and where necessary, data will also be listed. For continuous variables, data will be summarized with the number of patients (N), mean, standard deviation (SD), median, minimum, and maximum. For categorical variables, data will be tabulated with the number and proportion of patients for each category.

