4.2 Evaluable Population

The Evaluable Population includes all patients who receive at least 2 weeks of study treatment and complete the Week 3 Wound-QoL questionnaire.

The analyses of primary endpoint, secondary endpoints, and exploratory endpoints will be done in the evaluable population.

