5.1.5 Patient Disposition

Patient disposition will be summarized as indicated below using the Enrolled Analysis Population. The disposition categories will be summarized by number and percentage using the number of enrolled patients as a percentage denominator:

- Enrolled patients
- Safety population
- Evaluable population
- Completer population
-

Patient disposition information will be listed. In addition, patients who were discontinued from the treatment or who did not complete the treatment will also be presented in this listing, including early termination reason. A subject is considered a statistical completer (Evaluable population) if he/she receives at least 2 weeks of study treatment and completes the Week 3 Wound-QoL questionnaire.

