5.1.6 Protocol Deviations

Protocol deviations will be listed as well as summarized and grouped into different categories such as

- Violation of inclusion/ exclusion criteria
- Time schedule deviations
- Non-compliance based on the investigator or designee's compliance records in eCRF.
- Missing essential data such as incomplete wound-QoL questionnaire data
- Patient not discontinued as per protocol of study (in case of infection or treatment with prohibited medication)
- Other non-compliance

Multiple deviations can occur in the same patient and thus a patient can be counted in more than 1 deviation category.

Patient listings of protocol deviations will include reasons for non-compliance and will be sorted by site.

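### A one-day visit window discards usable Wound-QoL scores, and the SAP has no rule for a missing Week 5 score or an early-discontinuation score

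*SAP*

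**What the plan says.** The rule in SAP 5.1.4 is explicit: "Out of window and unscheduled assessments will be listed, but not used for descriptive analysis and calculation of primary and secondary endpoints". The window is one day either side for Weeks 2 to 5. For baseline, the SAP allows up to one week after screening, plus or minus one day; protocol 6.1 and 9.2.2 give one week plus or minus one day.

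The primary analysis (SAP 5.2.1) is a paired t-test of the change from baseline to Week 5 in the Evaluable Population. SAP 4.2: "The Evaluable Population includes all patients who receive at least 2 weeks of study treatment and complete the Week 3 Wound-QoL questionnaire". SAP 5.1.5 uses the same threshold: "A subject is considered a statistical completer (Evaluable population) if he/she receives at least 2 weeks of study treatment" and completes the Week 3 form. SAP 5.2.1 adds: "The primary endpoint analysis will also be repeated using the safety and completer populations".

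On missing data, SAP 5.1.2 asks for an early-discontinuation visit, gives item-level scoring rules (at least 13 of 17 valid items) and a replacement rule: "Patients who withdraw or are withdrawn before completion of the Week 2 assessments and the Week 3 Wound-QoL questionnaire will be replaced". Nothing there covers an absent Week 5 score.

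The protocol collects the early-discontinuation form under the Week 5 label. Its synopsis lists the questionnaire at Week 0 "and at Weeks 1 (baseline visit), 2, 3, 4, and 5 (end of treatment or early discontinuation visit"; Table 1 (footnote a) and section 9.2.5 agree. SAP 5.2.7.1 and 5.2.7.2 pair the two visits for vital signs and laboratory data. Protocol section 12 says: "The SAP will serve as a complement to the protocol and supersedes it in the case of any differences".

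**The concern.** Two gaps meet in the primary endpoint.

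First, the window removes scores that still measure nearly the intended period. A baseline form out of window costs more than one pair, because that patient then has no change score at any week.

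Second, a patient can enter the Evaluable Population at the Week 3 form and never give a usable Week 5 score. By default the paired t-test then uses observed pairs only. Some losses may relate to outcome: protocol 8.4.2 discontinues patients whose wound infection needs a prohibited medication, and protocol 7.3 lists adverse events as a reason for withdrawal. In a single-arm study, losing worse scores looks like improvement, with no control group to reveal it. The early-discontinuation form could reduce this bias, but its use is left open and could be settled after the data are seen.

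**Working it through.** **Inputs from the documents** (SAP 5.1.3): difference 0.35, SD of differences 0.88, two-sided alpha 0.05, paired t-test, N = 52. The documents give no dropout rate and no visit-timing data, so every rate below is an assumption.

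**1. The plan's own figure.** Power comes from the noncentral t distribution with n - 1 degrees of freedom and noncentrality (0.35/0.88) × √n. At n = 52 power is 80.3%; at n = 51 it is 79.5%. So 52 reproduces, as a number of usable pairs.

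**2. Fewer pairs.**

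| Usable pairs | 52 | 50 | 47 | 45 | 42 |
|---|---|---|---|---|---|
| Power | 80.3% | 78.7% | 76.1% | 74.2% | 71.1% |

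Losing 10% or 20% after the Week 3 form leaves 52 × 0.9 ≈ 47 or 52 × 0.8 ≈ 42 pairs. Keeping 52 pairs would need 52/0.9 ≈ 58 or 52/0.8 = 65 Evaluable patients.

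**3. Timing.** A Week 5 form two days late shares 7 - 2 = 5 recall days with an on-time form. Take visit-day error as normal, rounded to whole days, so that a form is out of window when the error exceeds 1.5 days. With SD 0.5, 0.75 or 1.0 day, 0.3%, 4.6% or 13.4% of Week 5 forms are lost, leaving about 52, 50 or 45 pairs. With a window of three days either side, the loss at SD 1.0 is 0.05%. If instead baseline and Week 5 each have a 5%, 10% or 15% chance of being out, 52 × 0.95², 52 × 0.90² and 52 × 0.85² leave about 47, 42 and 38 pairs, with power 76.1%, 71.1% and 66.6%.

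**4. Dropout related to response, leavers excluded.** Simulation with 20,000 replicates: 52 patients reach the Week 3 form; changes at Weeks 2 to 5 have SD 0.88 and common correlation 0.7; logistic dropout after Week 3 has slope 0.5, 1.0 or 1.5 per SD of the Week 3 change. Lower scores are better, so a negative mean is improvement. True change is 0, and false improvement should be 2.5%.

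| Assumed dropout | Mean change, observed pairs | False improvement |
|---|---|---|
| 5% | -0.01 to -0.04 | about 3% to 5% |
| 10% | -0.03 to -0.08 | about 4% to 8% |
| 20% | -0.06 to -0.14 | about 6% to 18% |

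At a true change of -0.35, the observed mean at 10% and 20% dropout runs from -0.38 to -0.49.

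**5. Same model, discontinuation score counted as Week 5.** If that score equals the Week 4 score, the bias at true change 0 is 0.00 and false improvement is about 2.5%. If it is 0.25 to 0.5 points worse than the Week 4 score, the mean at 10% and 20% dropout becomes +0.03 to +0.10. Counting helps only when the score is close to the patient's latest true state.

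**6. The three populations.** With discontinuation scores excluded, Safety, Evaluable and Completer give 47/47/47 pairs at 10% dropout or 42/42/42 at 20%. If three more patients miss only the Week 3 form, they give 50/47/50 or 45/42/45. Agreement among these tests says little about dropout bias. If the scores are counted, Evaluable gains the later leavers, and Safety also gains patients who left before the Week 3 form, so the analyses do differ.

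**The case against.** A strict prespecified window is a legitimate choice, and this one is clearly stated. At visit-day SDs of 0.5 and 0.75 it costs almost nothing; only SD 1.0 shows a visible loss. The deviation category "Time schedule deviations" in SAP 5.1.6 is one item in a generic list and does not show that slips are expected. All of this stands. It makes wider windows an inexpensive improvement, not the correction of an error.

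A reader might infer that the SAP simply discards early-discontinuation scores, since most fall outside the Week 5 window and the SAP prevails over the protocol. The documents do not support that. SAP 5.1.4 speaks of visits that are rescheduled and deviate, and an early-discontinuation visit is not plainly one. Protocol 9.2.6 treats unscheduled visits separately, Table 1 places the early-discontinuation visit in the final-visit column, and SAP 5.2.7 pairs it with Week 5. Counting it is at least as natural. The supportable statement is that both readings are open.

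The plan also gives some visibility: weekly scores in three populations (SAP 5.2.5), n for the primary endpoint, and listed termination reasons. These show that data are missing; they do not say how the missing data affect the Week 5 estimate.

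**Conclusion.** The point holds in two parts. The window rule removes usable scores, at a cost that depends on unknown visit timing. The SAP also leaves the missing Week 5 score and the early-discontinuation score without a rule, so the number of pairs and the meaning of the three t-tests are not fixed in advance.

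It would go too far to call the trial underpowered or its result biased. The sample-size arithmetic is right, and no loss rate is documented. The 18% false-improvement figure needs 20% dropout, the steepest slope and exclusion of discontinuation scores together; at 5% dropout it is about 3% to 5%. SAP 5.1.1 calls the inference exploratory, which limits the consequence, though this is the only planned hypothesis test. The change should be made before analysis; the study does not fail without it.

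**What to change.** Before analysis:

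1. In SAP 5.1.4, assign post-baseline Wound-QoL forms by study day (baseline = Day 0): Week 2 = Days 4-10, Week 3 = Days 11-17, Week 4 = Days 18-24, Week 5 = Days 25-31, taking the form closest to nominal Day 7, 14, 21 or 28 if there are two. Accept any pre-treatment Week 1 form as baseline. List forms before Day 4 or after Day 31 and use them only in the last-score analysis in step 2. Keep the strict one-day paired t-test as a sensitivity analysis.
2. State one rule for early-discontinuation scores: they count as Week 5 only on Days 25-31. Report the other reading, last collected score used as Week 5, as a sensitivity analysis in the Evaluable and Safety Populations.
3. Keep the paired t-test as primary. Add a supportive mixed model for repeated measures on Weeks 2 to 5 in the Safety Population (week as factor, baseline score, unstructured covariance), stating that it corrects only for dropout that depends on recorded scores.
4. Add an unfavourable-value or delta-adjusted analysis for patients with no Week 5 score. As an illustration, an observed mean of -0.35 with 20% missing and those patients 0.5 worse than baseline gives 0.8 × (-0.35) + 0.2 × 0.5 = -0.18. Setting missing changes to zero is not a substitute: it shrinks the mean and standard error together and leaves the p-value almost unchanged.
5. Report the number of Week 5 pairs in each population and state that the 80% power refers to 52 usable pairs.

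The cost is SAP wording, one model and three sensitivity analyses on data already collected, with slightly more variable assessment timing. The primary estimate stays pairs-only; the additions show how far dropout could move it.
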